9.3.2 Adverse Reaction and Suspected Adverse Reaction

An adverse reaction is any AE caused by the Study Drug.

A suspected adverse reaction is any AE for which there is a reasonable possibility that the drug caused the AE. A suspected adverse reaction implies a lesser degree of certainty about causality than an adverse reaction.

9.3.3 Serious Adverse Event (SAE)

A serious adverse event is any AE that in the view of either the Investigator or Sponsor, meets any of the following criteria:

- Results in death
- Is life threatening: that is, poses an immediate risk of death at the time of the event

 An AE or suspected adverse reaction is considered "life-threatening" if, in the view of
 either the Investigator or Sponsor, its occurrence places the patient at immediate risk of
 death. It does not include an AE or suspected adverse reaction that, had it occurred in a
 more severe form, might have caused death
- Requires inpatient hospitalization or prolongation of existing hospitalization
 Hospitalization is defined as an admission of greater than 24 hours to a medical facility and does not always qualify as an AE
- Results in a persistent or significant incapacity or substantial disruption of the ability to conduct normal life functions
- Results in a congenital anomaly or birth defect in the offspring of the patient (whether the patient is male or female)
- Important medical events that may not result in death, are not life-threatening, or do
 not require hospitalization may also be considered serious when, based upon
 appropriate medical judgment, they may jeopardize the patient and may require
 medical or surgical intervention to prevent 1 of the outcomes listed in this definition.
 Examples of such medical events include allergic bronchospasm requiring intensive
 treatment in an emergency room or at home, blood dyscrasias or convulsions that do

not result in inpatient hospitalization, or the development of drug dependency or drug abuse

9.4 Monitoring and Recording Adverse Events

Any pre-existing conditions or signs and/or symptoms present in a patient prior to the start of the Study (i.e., before informed consent) should be recorded as Medical History and not recorded as AEs unless the pre-existing condition worsened. The Investigator should always group signs and symptoms into a single term that constitutes a **single unifying diagnosis** if possible.

9.4.1 Serious Adverse Events

In the interest of patient safety, and in order to fulfill regulatory requirements, all SAEs (regardless of their relationship to Study Drug) should be reported to the Sponsor or designee within 24 hours of the Study Center's first knowledge of the event. The collection of SAEs will begin after the patient signs the informed consent form and stop at the end of the patient's follow-up period which is defined as Study Day 519 or the time of enrollment in $OLE\ Study\ BN40955$. When the Investigator is reporting by telephone, it is important to speak to someone in person versus leaving a message. An Initial Serious Adverse Event Form should be completed and a copy should be faxed to the Sponsor or designee. The fax number for reporting SAEs can be found in the Study Reference Manual.

Detailed information should be actively sought and included on Follow-Up Serious Adverse Event Forms as soon as additional information becomes available. All SAEs will be followed until resolution. SAEs that remain ongoing past the patient's last protocol-specified follow-up visit will be evaluated by the Investigator and Sponsor. If the Investigator and Sponsor agree the patient's condition is unlikely to resolve, the Investigator and Sponsor will determine the follow-up requirement.

9.4.2 Non-Serious Adverse Events

The recording of non-serious AEs will begin after the patient signs the informed consent form and will stop at the end of the patient's follow-up period, which is defined as Study Day 519 or the time of enrollment in $OLE\ Study\ BN40955$. The Investigator will monitor each patient closely and record all observed or volunteered AEs on the Adverse Event Case Report Form.

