2.5 Risk Assessment

The known potential risks to study participants associated with IT administration of RO7234292 are elaborated on in the Guidance to Investigator section of the Investigator's Brochure.

In brief, there are no apparently deleterious effects associated with reduction of *HTT* mRNA in normal adult mice or adult non-human primate (McBride et al. 2008; Boudreau et al. 2009; Drouet et al. 2009; McBride et al. 2011; Kordasiewicz et al. 2012). No abnormal behavioral deficits appear to result from heterozygous *HTT* inactivation by translocation in man, i.e., a 50% reduction in expression of the normal gene product (Ambrose et al. 1994); and silencing of both mutant *HTT* and wild-type *HTT* appears to dramatically improve HD-related behavioral abnormalities in HD mice models (Kordasiewicz et al. 2012).

Intrathecal administration of RO7234292 requires lumbar puncture (LP), which is associated with known risk for post-LP injection syndrome (e.g., headaches, nausea, vomiting, nerve irritation pain). Headache is the most common symptom, affecting up to 5-30% of participants. Headache usually resolves spontaneously within a few days, but in a minority of patients the headache can persist for weeks if untreated (Vandam and Dripps 1956; Costigan and Sprigge 1996; Turnbull and Shepherd 2003). The very rare risk for events of infection (e.g., meningitis) and hemorrhage (e.g., spinal hematoma) following LP are mitigated by protocol inclusion/exclusion criteria and study procedures.

Taking into account the measures taken to minimize risk to subjects participating in this study, the potential risks identified in association with RO7234292 are justified by the anticipated benefits that may be afforded to patients with HD.

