6.1.1 Screening Period (Week -4 to Week -1)

Written informed consent for the study will be obtained prior to the performance of any study-related procedures including screening procedures. During the Screening Period, inclusion/exclusion criteria will be evaluated to determine patient eligibility for the study. A single CSF sample will be collected during the Screening Period. At least 2 weeks must elapse between the screening CSF collection and Study Day 1. Abnormal laboratory screening results may be retested for review by the Study Medical Monitor for eligibility purposes.

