6.2.18 Collection of CSF

Patients will have CSF collected at the Screening Visit, prior to administration of each dose of RO7234292 and at the Post-Treatment Visit. At each collection, 20 mL of CSF fluid is to be collected for analyses. If there are difficulties in collecting 20 mL of CSF fluid, a minimum of 15 mL should be collected. A 24G atraumatic needle (Whitacre or other if approved by Sponsor prior to use) will be used. Depending on institutional guidelines, local anesthesia may be used for the procedure. Sedation may not be used. Spinal ultrasound may be used for the LP procedure, if deemed necessary, but is not required.

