8.4 Treatment Precautions

Patients will be discouraged from resting supine after the lumbar puncture procedure and will be encouraged to mobilize immediately.

Throughout the study, patients will be monitored for post-LP headache and for any signs or symptoms of infection. The Study Manual will provide guidance for site personnel on differentiating between and managing treatment of pressure headaches and encephalitic/meningitic headaches.

Epinephrine for subcutaneous injection, diphenhydramine for intravenous injection and any other medications and resuscitation equipment for the emergency management of anaphylactic reactions must be close to the location where the injection is being performed.

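### For patients who do not enter BN40955, the last lumbar puncture falls at the last scheduled contact, on the nominal day that adverse event collection ends

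*Combined protocol and SAP*

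**What the plan says.** Section 6.2.18 sets out the lumbar punctures (LPs): "Patients will have CSF collected at the Screening Visit, prior to administration of each dose of RO7234292 and at the Post-Treatment Visit". In Appendix A the last of these is at the Day 519/ET visit, the final column of the schedule. Section 3.4.3 and the Appendix A footnote limit that visit to patients who do not enter BN40955.

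Section 9.4.1 has collection of serious adverse events (SAEs) "stop at the end of the patient's follow-up period which is defined as Study Day 519 or the time of enrollment in" Study BN40955. Section 9.4.2 says that recording of non-serious events "will stop at the end of the patient's follow-up period, which is defined as Study Day 519", or at enrolment in the same study. Both windows open at consent. Section 9.4.1 adds that SAEs are followed until they resolve, past the last visit if need be.

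Section 2.5 names headache, infection and haemorrhage as LP risks. On headache it says: "Headache is the most common symptom, affecting up to 5-30% of participants", usually gone in a few days but lasting weeks in a minority. Section 8.4 says: "Throughout the study, patients will be monitored for post-LP headache and for any signs or symptoms of infection". The synopsis adds telephone monitoring between clinic visits.

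Appendix A gives the Day 519 visit a window of ±21 days. For early terminators, Sections 6.1.3, 8.8 and 8.9 move the same visit to about 14 weeks after the patient's own last dose. On the Screening LP, Section 6.1.1 says: "At least 2 weeks must elapse between the screening CSF collection and Study Day 1".

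**The concern.** The protocol treats LP complications as foreseeable and schedules contact after every dosing LP to find them. The final LP is the exception. It is done at the last contact, on the nominal day that collection closes, so a complication that appears the next day or later has neither a scheduled question to reveal it nor an open window to record it. That includes a delayed infection or spinal bleed, which could be serious.

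The stop rule is also ambiguous. Study Day 519 is the name of a visit that can move and, at the same time, the date on which recording stops. Two sites could apply it differently to the same patient. Safety and tolerability is the primary objective, and the risk here comes from a procedure that the study itself requires.

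**Working it through.** **1. The plan's own figure.** Last dosing visit Day 421, final visit Day 519 (Appendix A): 519 − 421 = 98 days = 14.0 weeks. This agrees with Section 3.4.3.

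**2. Scheduled contact after each LP (Appendix A).**

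| LP | Next contacts | Days after LP |
|---|---|---|
| Screening | Day −1 | 13 to 28 (step 5) |
| Day 1 | Days 2, 3, 8 | 1, 2, 7 |
| Day 29 | Days 30, 36 | 1, 7 |
| Each Maintenance dose (e.g. Day 421) | Days 422, 428 | 1, 7 |
| Day 519/ET | none | none |

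A patient who enters BN40955 has no Day 519 LP. That patient's last LP in this study, on Day 421, has both calls.

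**3. Collection left after the final LP, under each reading of Study Day 519.** Calendar reading: days left = 519 − day of LP. Visit-label reading: collection ends with the visit, so 0 days are left for everyone.

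| Case | Day of LP | Calendar reading | Visit-label reading |
|---|---|---|---|
| On time | 519 | 0 | 0 |
| Earliest in window | 519 − 21 = 498 | 21 | 0 |
| Latest in window | 519 + 21 = 540 | −21 (closed before the LP) | 0 |
| ET, last dose Day 253 | 253 + 98 = 351 | 168 | 0 |
| ET, last dose Day 393, seen 21 days late | 393 + 98 + 21 = 512 | 7 | 0 |

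The on-time patient has nothing left under either reading. The other rows depend on the reading chosen.

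**4. Size.** Neither the number of final LPs nor a rate per LP is given. Section 2.5 states 5-30% of participants. Assume that this applies to a single LP; expected headaches = n × rate.

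| Final LPs (n) | At 5% | At 30% |
|---|---|---|
| 10 | 0.5 | 3.0 |
| 23 | 1.15 | 6.9 |
| 46 (ceiling) | 2.3 | 13.8 |

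With 10 final LPs, the chance of at least one headache is 1 − 0.95^10 = 0.40 at the low end and 1 − 0.70^10 = 0.97 at the high end. These counts include same-day onsets, which would be collected, so they overstate what is lost.

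**5. Screening LP.** Section 6.1.2 makes Day −1 the day before Day 1, so there is no Day 0. The latest permitted LP is Day −14, which is 14 − 1 = 13 days before the Day −1 visit. The earliest is Day −29, which is 29 − 1 = 28 days before it.

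**The case against.** Several passages might seem to close the gap.

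- *Monitoring throughout the study (Section 8.4).* The Study Glossary ends on-study status at the patient's last study visit, so this does not reach past the final LP.
- *Telephone monitoring between clinic visits (synopsis).* Nothing lies between the last visit and a later one. It could cover the Screening interval, but Appendix A lists no call there.
- *Following SAEs to resolution (Section 9.4.1).* This applies to SAEs already collected, not to one that starts later.
- *Extra visits for adverse events (Sections 3.4 and 6.1).* Someone must first learn of the event.

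Other parts of the opposing case stand.

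- A reader might infer that complications of the final LP are neither collected nor followed. That is too strong: Appendix A captures events at the visit itself, and an SAE recorded then is followed.
- A reader might also infer both that a Day 540 LP falls after closure and that no early terminator contributes post-LP data. The first needs the calendar reading and the second the visit-label reading; they cannot both hold.
- The final LP gives no drug and comes 14 weeks after the last dose. Each patient who completes dosing has 9 (2 + 7) or 16 (2 + 14) dosing LPs with follow-up contact, so LP tolerability is otherwise well observed.
- The Screening LP is not outside collection. Recording runs from consent, and events are asked about on Day −1.

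**Conclusion.** The point holds in a limited form. For a patient who does not enter BN40955 and attends on time, an LP complication that starts after the day of the final visit is outside adverse event and SAE collection, and no contact is scheduled that would find it. This is so on either reading of Study Day 519. Separately, that label gives conflicting cut-offs: as a calendar day, it closes collection before an LP on Days 520-540, yet leaves it open after most early termination visits, with no contact scheduled in the open time.

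The size cannot be fixed from the documents. Per 10 final LPs, 0.5 to 3 headaches are expected if 5-30% applies per LP, less the same-day onsets. A figure for all 46 patients is a ceiling and not an estimate, because patients who roll over have no final LP.

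The Screening LP is a secondary point about contact and recall: 13 to 28 days without a listed contact, and none at all for a patient who fails screening after the LP. Such a patient has no Study Day 1, and so no Day 519 to end collection.

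This concerns completeness of safety capture. It does not touch sample size, power or type I error, and the effect on the regimen summaries is likely to be small. The correction is worth making because it is cheap.

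**What to change.** 1. In Sections 9.4.1 and 9.4.2, state that collection ends at the latest of the actual final visit, 14 weeks after the last dose, and 7 days after the last study LP, or at enrolment in BN40955. The 14-week term keeps the window from being cut short for an early terminator who declines the ET visit. For a patient who is never dosed, that term drops out and the others still give an end date. The 7 days match the protocol's own last call after a dosing LP; they are not derived from onset data.
2. In Appendix A, add the existing next-day and 7-day adverse event and concomitant medication calls after the Day 519/ET LP. Add the same calls after the Screening LP, including for patients who then fail screening.
3. Reconcile the synopsis statement on telephone monitoring, Section 8.4 and Appendix A, so that each promise of monitoring has a scheduled contact behind it.

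The cost is at most four short calls per patient (two per LP), and the last patient's data close about a week later. There is one trade-off. If the sponsor means Day 519 as a calendar date for early terminators, the new rule shortens their open window: in the Day 253 example, from 168 days after the ET visit to 7. If that longer window is wanted, calendar Day 519 can be kept as a fourth term.

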9.4.3 Evaluation of Adverse Events (Serious and Non-Serious)

The Investigator's opinion of the following should be documented on the Adverse Event Case Report Form:

9.4.3.1 Relationship to the Study Drug

The event's relationship to the RO7234292 is characterized by 1 of the following:

- Related: There is clear evidence that the event is related to the use of Study Drug, e.g., confirmation by positive re-challenge test
- **Possible:** The event cannot be explained by the patient's medical condition, concomitant therapy, or other causes, and there is a plausible temporal relationship between the event and *RO7234292* administration
- Unlikely/Remote: An event for which an alternative explanation is more likely
 (e.g., concomitant medications or ongoing medical conditions) or the temporal
 relationship to RO7234292 administration and/or exposure suggests that a causal
 relationship is unlikely (For reporting purposes, Unlikely/Remote will be grouped
 together with Not Related)
- Not Related: The event can be readily explained by the patient's underlying medical condition, concomitant therapy, or other causes, and therefore, the Investigator believes no relationship exists between the event and Study Drug

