Study Design	This is an open-label extension (OLE) of Study ISIS 443139-CS1. Study ISIS 443139-CS1 was a multiple-ascending dose (MAD) study in 46 patients with early manifest HD aged 25-65 years, inclusive. In the MAD study, patients received 4 doses of ISIS 443139 or placebo. Eligibility for Study $BN40697$ (ISIS 443139-CS2) is based on completion of the 4-dose Treatment Period of the prior MAD study and absence of deterioration in health or intervening activities that would introduce risk to the patient sufficient to preclude participation in the OLE.
	This is a multi-center study with study duration of up to 18 calendar months. Two (2) dosing regimens will be tested – monthly and bimonthly. Randomization between regimens (1:1) will be stratified by Study Center.
	 "Monthly" regimen: administrations of RO7234292 every 28 days for 62 weeks (2-dose Loading Period followed by 14-dose Maintenance Period)
	 "Bimonthly" regimen: 2 administrations of RO7234292 separated by 28 days (2-dose Loading Period) followed by administrations every 56 days for 56 weeks (7-dose Maintenance Period)

Study Design Continued	The $RO7234292$ doses used in these regimens will not exceed 120 mg/dose, the highest dose evaluated in the prior MAD study.
	A final visit will be held approximately 14 weeks after the last dose.
	The extent of screening procedures required for this study varies depending on the amount of time that has elapsed between participation in the MAD study and the start of the OLE (see Appendix A, Schedule of Procedures).
Number of Subjects	Up to 46 (patients who previously participated in ISIS 443139-CS1)
Study Population	Inclusion Criteria
	Signed Written Informed Consent
	Must have given written informed consent (signed and dated) and any authorizations required by local law and be able to comply with all study requirements
	Must be capable of giving informed consent (in the opinion of the Investigator)
	Target Population
	3. Must have completed the Treatment Period of Study ISIS 443139-CS1
	Able and willing to meet all study requirements in the opinion of the Investigator, including:
	Adequately supportive psychosocial circumstances

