10.6.2 Safety Analysis

The safety analysis will be conducted on the Safety Population.

Treatment duration and amount of RO7234292 received will be summarized by regimen.

All treatment-emergent adverse events (TEAEs) and SAEs will be summarized for each regimen and for all patients using the Medical Dictionary for Regulatory Activities (MedDRA) coding system by system organ class, preferred term, relationship to Study Drug, and severity.

Narratives of "on-study" deaths, serious and significant AEs, including early withdrawals due to AEs, will be provided.

Laboratory tests to ensure patient safety including chemistry panel, hematology panel, CSF safety labs (cell counts, protein, glucose) and urinalysis, will be summarized by study visit for each regimen. These safety variables will also be presented as change and percent change from baseline over time, as appropriate.

Vital sign and ECG measures will be tabulated by regimen. In addition, the number of patients who experience abnormalities in clinical laboratory evaluations will be summarized by regimen.

Columbia – Suicide Severity Rating Scale will be summarized by study visit for each regimen. Physical examination, standard neurological assessment (including fundi), and clinical and neuroimaging results will be summarized, if appropriate, and listed.

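### Adverse-event causality is rated against study drug only, with no rule for lumbar-puncture events, and the by-regimen safety tables do not relate such events to 16 versus 9 dosing punctures

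*Combined protocol and SAP*

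**What the plan says.** The primary objective (section 1.1) is the safety and tolerability of monthly and bimonthly intrathecal administration. Section 8.1 makes an LP part of every dose. Section 2.5 names a post-LP syndrome of headache, nausea, vomiting and nerve irritation pain, and says of it: "Headache is the most common symptom, affecting up to 5-30% of participants".

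Section 9.4.3.1 sets the causality rating: "The event's relationship to the RO7234292 is characterized by 1 of the following". There are four levels.

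- Related needs clear evidence of a link to use of the drug.
- Possible applies when "The event cannot be explained by the patient's medical condition, concomitant therapy, or other causes" and the timing is plausible.
- Unlikely/Remote applies when an alternative explanation is more likely. The section adds "For reporting purposes, Unlikely/Remote will be grouped" with Not Related.
- Not Related applies when "The event can be readily explained by the patient's underlying medical condition, concomitant therapy, or other causes" and the investigator therefore sees no relationship.

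Sections 9.4.3.1 to 9.4.3.5 contain no item for relationship to the procedure. Section 10.6.2 summarizes treatment-emergent events (TEAEs) for each regimen and overall "by system organ class, preferred term, relationship to Study Drug, and severity". It mentions neither LP attribution nor a per-puncture rate.

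**The concern.** The LP is a known cause of events, and the two regimens differ in how many LPs they involve. A headache after dosing may come from the puncture, the drug or neither, and the form records a judgment on the drug only. Two problems follow.

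First, centers may rate the same LP event differently. If most rate it Not Related, the relationship table leaves out harm that comes from the intrathecal route. If some rate it Related, the table mixes drug and puncture effects in unknown proportion.

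Second, the by-regimen tables will tend to show more LP-type events under Monthly dosing even if the drug adds nothing, and the plan gives the reader no means of setting that excess against the number of punctures.

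**Working it through.** **Puncture counts.** The plan's dose counts reproduce from the visit tables in Appendix A, footnote 1.

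- Monthly maintenance: Days 57 to 421 every 28 days, (421 − 57)/28 + 1 = 14. With loading doses on Days 1 and 29, 14 + 2 = 16.
- Bimonthly maintenance: Days 85 to 421 every 56 days, (421 − 85)/56 + 1 = 7. With loading, 7 + 2 = 9.
- Appendix C limits maintenance CSF sampling to dosing visits, so Bimonthly patients have no LP at their other visits. Dose and dosing LP match one to one in both arms.
- Adding the Screening and Post-Treatment draws gives 18 vs 11 scheduled LPs, or 17 vs 10 for patients who move to Study BN40955.

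**How an LP event would be rated.** If the investigator judges that the puncture explains the event, Possible is closed, because it requires that no other cause explains the event. Not Related or Unlikely/Remote fits most naturally. Related stays open to someone who counts intrathecal delivery as use of the drug. No section settles the choice.

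**Expected size with no drug effect.** Let p be the chance of an LP event per puncture, the same in both arms. Expected events per patient are 16p and 9p, a ratio of 16/9 = 1.78 for any p. If punctures are independent, the proportion of patients with at least one event is 1 − (1 − p)^k, with k = 16 or 9.

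| Assumed p | Monthly | Bimonthly | Difference (points) | Events per patient |
|---|---|---|---|---|
| 1% | 14.9% | 8.6% | 6 | 0.16 vs 0.09 |
| 5% | 56.0% | 37.0% | 19 | 0.80 vs 0.45 |
| 10% | 81.5% | 61.3% | 20 | 1.60 vs 0.90 |
| 30% | 99.7% | 96.0% | 4 | 4.80 vs 2.70 |

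With 23 patients per arm (46 split 1:1, all doses given), the expected Monthly excess is 23 × 7 × p: about 8 events at 5% and 48 at 30%.

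**Unit of the headache figure.** The 5-30% in section 2.5 is per participant, and the plan gives no per-puncture rate, so every p above is an assumption. If 5% or 30% were instead the chance over nine punctures, then p = 1 − (1 − 0.05)^(1/9) = 0.57% or 1 − (1 − 0.30)^(1/9) = 3.9%. Over 16 punctures that gives 8.7% or 47.0%.

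**Pre-dose information.** Each patient has one Screening LP at least two weeks before Day 1 (section 6.1.1), and section 9.4.2 states: "The recording of non-serious AEs will begin after the patient signs the informed consent form". That gives at most 46 punctures. Even 0 events in 46 leaves a one-sided 95% upper limit of 1 − 0.05^(1/46) = 6.3%.

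**The case against.** The case against has five parts.

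**The rating is not fixed by the text.** A reader might infer that LP events must be classed as Not Related. The documents do not say so: that category also requires the investigator to believe there is no relationship, and Related and Possible are worded around use and administration of the drug. This stands. The defect is an undefined rule, not a stated misclassification.

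**The events are not hidden.** Section 10.6.2 covers all TEAEs by preferred term whatever their rating, section 9.4 asks for one unifying diagnosis where possible, and section 8.4 has patients monitored for post-LP headache. A recognized post-LP headache will be visible by regimen. This stands, but nausea, vomiting and pain are not specific to the puncture, and monitoring without a field for the judgment loses it. Section 8.4 also refers to a Study Manual on telling headache types apart. That manual is not among the documents and might address attribution.

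**Separating drug from puncture is not a stated objective.** Sections 2.4 and 10.6 support this: bimonthly dosing is there to test pharmacological effect, and formal regimen comparison is optional. A reader might infer that the choice of regimen turns on this separation; the documents do not say that. The by-regimen safety summaries are nevertheless planned and serve the primary objective.

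**Higher Monthly counts are not assured.** Under the model above with 23 per arm, the number of Monthly patients with an event is strictly higher with probability 0.88 at p = 5% and 0.58 at p = 30%. Events may also cluster within patients. The 1.78 ratio concerns expected event counts only.

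**The fix does not break the confounding.** Because each dose comes with one LP, events per dosing LP equal events per dose. This stands in full and limits what can be claimed for the remedy.

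**Conclusion.** The point holds as a gap in attribution and reporting. Causality is rated against drug only, LP events have no rating rule, and the relationship table may therefore omit or inconsistently include harm from the intrathecal route. The by-regimen tables carry a 1.78-fold difference in dosing punctures that the plan neither attributes nor relates to puncture count.

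The ratio assumes full dosing and an equal per-LP rate in both arms. The patient-level proportions also assume independent punctures and a chosen rate, and the gap ranges from about 4 to 20 points over 1% to 30% per LP.

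A stronger reading would be that the rating scale itself makes drug and puncture effects inseparable. The documents do not support it: the confounding comes from giving one LP with each dose, and no rating scale creates or removes it.

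**What to change.** - **eCRF and section 9.4.3.1:** add a separate adverse-event item, relationship to lumbar puncture/intrathecal procedure, with the same four levels, rated independently of study drug. State that LP events are rated on it.
- **Section 10.6.2:** tabulate TEAEs by regimen and LP relationship. For the post-LP terms in section 2.5, report events per LP performed as well as per patient.
- **Optional context:** tabulate events between the Screening LP and Day 1. Label them pre-dose context and not a control: there are at most 46 punctures, no injection is given, and patients may have had ISIS 443139 in the earlier study.
- **Limits to state in the report:** dose and dosing LP match one to one, so these steps improve attribution but leave drug and puncture confounded between regimens. Flag any attribution entered after the fact as retrospective, since investigators will know the regimen and the outcome.

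The cost is one eCRF field, query work for events already recorded, and one or two tables. No visit, procedure or treatment rule changes.
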